6.3 Recruitment

Participants will contact the research team via email in response to the recruitment advertisements if they are interested in taking part in the study.

6.4 Payment

Participants will be reimbursed for their time at a rate equivalent to £10.55/hour. The total time commitment for each participant is 34 hours. The payment to participants on successful completion of the whole study will be £360. It is essential that participants attend on time for all blood tests across both experiments, therefore, participants will only be paid on successful completion of all aspects of the study. If a participant completes the baseline visit but does not complete experimental visits they will be paid £40. If a participant successfully completes the optional stool sampling assessments they will receive an additional £20. The total potential reimbursement is therefore £380.

6.5 Pre-screening

Prior to the pre-screen, the participant will be emailed a Participant Information Sheet (PIS). This will be done at least 24 hours before the experimental visit. Potential participants will be allowed as much time as need to decide to whether or not to participate. They will then be contacted by one of the researchers by telephone and asked to answer questions relating to their eligibility for the study. They will have the opportunity to ask the researcher questions about the study during the call. If the participants' responses are satisfactory, the participant will be invited for a screening visit.

6.6 Screening

The screening visit will be held at the King's CRF. It will be performed no longer than 28 days prior to IMP administration.

- Gaining informed consent
- Recording demographic details: sex, date-of-birth, ethnicity, previous medical history, medication history, and alcohol and substance use history
- Recording vital signs, height, weight, BMI and body fat content
- Urine drug screen for illicit drug use and pregnancy
- Urinalysis, alcohol breath test
- Blood tests: full blood count (FBC), urea and electrolytes (U&Es) and liver function tests (LFTs)
- Stool sample provided to take home (optional)

6.7 Consent

Informed consent will be obtained prior to the participant undergoing procedures that are specifically for the purposes of the trial. The right of a participant to refuse participation without giving reasons will be respected. The participant will remain free to withdraw at any time from the trial without giving reasons. They will be provided with a contact point where they may obtain further information about the trial. Potential participants should be able to give consent and a person is assumed to have mental capacity to make a decision unless it is shown to be absent. Consent will be taken by medical doctors who are duly authorised, trained and competent to participate according to the ethically approved protocol, principles of Good Clinical Practice (GCP) and Declaration of Helsinki.

Written material consisting of participant information leaflet and consent documentation will be approved by the Research Ethics Committee and will be in compliance with GCP, local regulatory and legal requirements. There will be opportunity for the participant to ask questions to a member of the research team. The patient will be given as much time as required to consider the information and consider their participation. A copy of the consent form and PIS will be given to the participant, with

the original consent filed in the investigator site file and a copy of the consent form in the Case Report Form.

6.8 Randomisation

Subjects will be randomised into the study provided they have satisfied all subject selection criteria. A web based randomisation system will be designed, using the bespoke King's Clinical Trials Unit (KCTU) randomisation system and will ensure each treatment is equally distributed across each study period. The randomisation system will be created in collaboration with the study team and maintained by the KCTU for the duration of the project. It will be hosted on a dedicated server within KCL. The Chief Investigator (CI) or delegate will request usernames and passwords from the KCTU. System access will be strictly restricted through user-specific passwords to the authorised research team members. It is a legal requirement that passwords to the randomisation system are not shared, and that only those authorised to access the system are allowed to do so. If new staff members join the study, a user-specific username and password must be requested via the CI or delegate from the KCTU team and a request for access to be revoked must be requested when staff members leave the project. Study site staff experiencing issues with system access or functionality should contact the CI or delegate in the first instance.

Participant initials and date of birth will be entered on the randomisation system, NHS number, email addresses, participant names and addresses and full postcodes will not be entered into the randomisation system. No data will be entered onto the randomisation system unless a participant has signed a consent form to participate in the study. Randomisation will be undertaken by authorised staff onto the randomisation system by going to www.ctu.co.uk and clicking the link to access the randomisation system. A full audit trail of data entry will be automatically date and time stamped, alongside information about the user making the entry within the system.

The CI team will undertake appropriate reviews of the entered data, for the purpose of data cleaning. No data can be amended in the system, however CI or delegate may request King's Clinical Trials Unit to add notes against individual subject entries to clarify data entry errors. Upon request, KCTU will provide a copy of the final exported dataset to the CI in .csv format and the CI will onward distribute as appropriate.

6.9 Blinding and Emergency Unblinding

The study will be double-blind with unblinding occurring at the end of data collection on approval by the Principal Investigator. The capsules will be identical in appearance so both the investigators and participants will remain blinded to treatment allocation. The Maudsley pharmacy will hold treatment allocation information for each participant, with 24-hour non-resident on-call access and can be called at any time to unblind a specific session.

Participants will be monitored before and after dosing and not discharged until medically cleared. Delayed adverse effects to study medications after discharge are unlikely, however, if required emergency unblinding will be provided by the on-call pharmacist. Unblinding protocol and reporting will be applied according to the local pharmacy procedures.

Out of Hours Emergency Contact

Participants will be provided with a contact card when receiving the study medication, so that they can contact the investigators in case of emergency out of hours. The investigator will contact the on-call pharmacist if unblinding is required. Participants will also be instructed to dial 999 or 111 in case of emergency.

6.10 Withdrawal criteria

- i. Withdrawal of consent
- ii. Significant abnormalities detected during the medical assessment or blood tests at the screening visit
- iii. Use of alcohol, illicit substances 24hour before or during experiments
- iv. Use of over-the counter medications, health supplements or CBD products
- v. Use of prescribed medications (excluding the intrauterine device or intrauterine system)
- vi. Suspected Unexpected Serious Adverse Reaction
- vii. Participant does not attend follow-up point
- viii. Investigator discretion

Participants have the right to withdraw from the study at any time for any reason. The investigator also has the right to withdraw participants from the study drug in the event of inter-current illness, AEs, SAEs, SUSARs, protocol violations, cure, administrative reasons or other reasons. It is understood by all concerned that an excessive rate of withdrawals can render the study un-interpretable; therefore, unnecessary withdrawal of participants should be avoided. Should a participant decide to withdraw from the study, all efforts will be made to report the reason for withdrawal as thoroughly as possible. Withdrawn participants will be replaced.

6. 11 Expected duration of the trial

The end of trial will be defined as the database lock.

7. TRIAL PROCEDURES

7.1 Setting

NIHR-Wellcome Trust Kings Clinical Research Facility (CRF)

7.2 Eligibility Review

The study team will review participants eligibility for the study at the start of each experimental visit. This will include a urine drug screen and alcohol breath test.

7.3 Fasting Requirements

Participants will fast from 10pm the previous evening and will not eat until 4 hours after drug administration on the first day of each experimental visit. Participants will be allowed to drink water only.

7.4 Administration

Drug administration will be at approximately 9am on the first day of each experiment. Oral administration.

Participants will not be informed which formulation of drug they are being administered.

7.5 Trial assessments

7.5.1 Blood sampling

Blood samples will be drawn at the following time-points on experimental visits: Pre-dose (0-5mins), 0.5, 1, 2, 3, 4, 5, 6, 8, 24, and 48hrs post-dose. The 24hr and 48hour samples should be taken within 15minutes of the target time.

7.5.2 Vital signs

Vital signs (HR, RR, BP, Temp) will be recorded on experimental visits at the following times: pre-dose and 1, 2, 4, 8, 24 and 48hrs post-dose. Urinalysis will be completed 4hrs post-dose. The 24hr and 48hour readings should be taken within 15minutes of the target time.

7.5.3 Adverse events

Participants will be asked to report adverse events at each blood sampling timepoint i.e. pre-dose (0-5mins), 0.5, 1, 2, 3, 4, 5, 6, 8, 24, 48hrs post-dose and at the 7-14 day follow-up visit. Participants will be asked specifically about adverse events including, but not limited to, anxiety, irritability, somnolence, dizziness, disorientation, nausea, abdominal pain, abdominal distension, diarrhoea, vomiting, and flatulence.

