We have selected a dose of 1000mg/day of the novel (formulation of CBD SEEK-CBD) for the proposed study because we plan to use this dose and formulation in subsequent clinical trials in patients with schizophrenia. This is therefore the appropriate dose for collecting pharmacokinetic data prior to its use in patients. Establishing its bioavailability empirically is particularly important, as CBD does not demonstrate dose-proportionality. (C_{max} slope 0.73; AUC_t slope 0.64).(Taylor et al. 2018)

A 7-fold increase in CBD exposure with 1000mg of SEEK-CBD would be dose equivalent to a 4-5 fold increase in exposure with 1500mg of regular CBD following a meal. In a study by Taylor et al (8), healthy volunteers received a single oral dose of conventional 1500 mg CBD in either the fed (high-fat breakfast) or fasted state. Food increased C_{max} by 4.85-fold (95% CI: 4.01–5.87) and AUC_t by 4.2-fold (90% CI 3.63–4.85). Critically, this study found that ‘there was no worsening in the severity of TEAEs in the fed state [compared to the unfed state], hence there is no appreciable safety concern’. Moreover, there were no serious adverse events: the most common were nausea, headache, and somnolence.

Several features of the proposed study's design will ensure the safety of the participants. The drugs will be administered in a state of the art NIHR Clinical Research Facility at King's College Hospital, which is purpose-built for pharmacokinetic studies of novel compounds. Adverse events will be monitored regularly, with medical staff will be on hand at all times. Participants will only leave the facility when all clinical and physiological measures are normal, and will be able to contact the investigators at any time after they leave. Participants will be able to remain in hospital overnight if required. The safety blood tests (LFTs, U&Es, FBC) are taken 4 hours post-dosing and the results will be available within 24 hours. If unexpected adverse events do arise, subsequent experimental sessions can be suspended and the study drug dose can be reduced. This contingency has been explicitly incorporated into the protocol (see section 9.5). We have also limited the maximum number of dosing sessions per day to three, so that action can be taken before multiple participants receive the study drug.

The gut microbiome and the endocannabinoid system

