9.2 Investigator Assessment

The investigator will seek information on adverse events from participants at 8 hours, 24 hours and 48 hours after each drug administration. Participants will also be able to spontaneously report adverse events throughout the lifetime of the trial. The investigator will use specific questioning and, as appropriate, examination. Information elicited will be recorded participant's Case Report Form. All

clearly related signs, symptoms, and abnormal diagnostic procedures will be recorded. The clinical course of each event should be followed until resolution or stabilisation.

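### Headache, among the most common events in a study the protocol cites for safety, is not on the list of symptoms asked about by name and may be under-recorded

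*Protocol*

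**What the plan says.** Protocol section 3, in the rationale for the dose, describes a study in which "healthy volunteers received a single oral dose of conventional 1500 mg CBD in either the fed (high-fat breakfast) or fasted state". It reports that "there were no serious adverse events: the most common were nausea, headache, and somnolence".

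Protocol 7.5.3 sets out the adverse-event enquiry in two steps. The first is general: "Participants will be asked to report adverse events at each blood sampling timepoint", and again at the follow-up visit. The second is specific: "Participants will be asked specifically about adverse events including, but not limited to" the following: "anxiety, irritability, somnolence, dizziness, disorientation, nausea, abdominal pain, abdominal distension, diarrhoea, vomiting, and flatulence". SAP 8.3 repeats both steps with the same list. Protocol 9.2 adds that "Participants will also be able to spontaneously report adverse events throughout the lifetime of the trial".

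Protocol 10.3 and SAP 10.6.7 plan tables of treatment-emergent events by system organ class and preferred term, by treatment, by relationship and by severity. Neither section distinguishes events elicited by a named prompt from events the participant volunteered.

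**The concern.** The protocol identifies three events as the most common in a study close to this one in population and single-dose design, then asks about two of them by name and leaves the third to a general question. A symptom put to a participant by name tends to be reported more completely than one the participant has to bring up. If that happens here, headache could look rarer than nausea or somnolence for a reason that has nothing to do with the drug, and a reader of the tables could not tell.

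What is at stake is limited to the absolute headache count and how it reads beside other symptoms. That count has some uses. Protocol 9.5 lets the Principal Investigator take the incidence and severity of adverse effects into account when deciding whether to pause the study or change the dose. Protocol 9.4 sets no stopping rules and section 11 provides for no monitoring committee, so the recorded events are what that decision has to go on. Section 3 also says that the same dose and formulation are intended for later patient trials. An event that is never elicited cannot be recovered at analysis.

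**Working it through.** The plan states no figure to reproduce, so the main check is a comparison of the texts.

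**1. Cited events against named prompts.** The list in protocol 7.5.3, identical in SAP 8.3, has 11 terms.

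| Event cited in protocol section 3 | Named in protocol 7.5.3 | Named in SAP 8.3 |
|---|---|---|
| Nausea | yes | yes |
| Headache | no | no |
| Somnolence | yes | yes |

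Two of the three cited events are prompted by name. Six of the 11 terms are gastrointestinal (nausea, abdominal pain, abdominal distension, diarrhoea, vomiting, flatulence), and protocol 7.5.5 adds a separate gastrointestinal rating scale. No described instrument has a headache item.

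**2. Other routes for capturing headache.** There are three: the open wording of the list, the general enquiry, and spontaneous reporting. How often the general enquiry is made is not settled. Protocol 7.5.3 puts it at all 11 blood sampling times and at follow-up. Protocol 9.2 and the visit schedule in 7.7.3 give 8, 24 and 48 hours. That is a separate inconsistency to be reconciled. A general enquiry exists on either reading, but on the second there are fewer chances to mention a short-lived headache.

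**3. Scale, for illustration only.** Inputs:
- n = 12 complete datasets (protocol 10.2, SAP 10.2).
- p = true proportion of participants with headache after one dose. Not in the documents; assumed 10% to 40%.
- s = share of those headaches recorded without a named prompt. Not in the documents; assumed 0.5 to 1.0.

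Expected participants with headache recorded per formulation = n × p × s. Chance of recording at least one = 1 − (1 − p × s)^n.

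| p | s = 1.0 | s = 0.75 | s = 0.5 |
|---|---|---|---|
| 10% | 1.2 (0.72) | 0.9 (0.61) | 0.6 (0.46) |
| 20% | 2.4 (0.93) | 1.8 (0.86) | 1.2 (0.72) |
| 30% | 3.6 (0.99) | 2.7 (0.95) | 1.8 (0.86) |
| 40% | 4.8 (1.00) | 3.6 (0.99) | 2.4 (0.93) |

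Cells show the expected count, with the chance of at least one report in brackets. Example: 12 × 0.20 × 0.5 = 1.2, and 1 − (1 − 0.10)^12 = 0.72. With the 14 participants planned for recruitment, the expected counts run from 1.4 to 5.6 at full capture and from 0.7 to 2.8 at half capture.

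Between full and half capture the difference at n = 12 is 0.6 (1.2 − 0.6) to 2.4 (4.8 − 2.4) participants per formulation. This shows what an assumed capture fraction would do. It is not evidence that any loss occurs.

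**4. Effect on the formulation comparison.** The same list is used for both formulations under blinding, so s can be taken as equal in the two. With true proportions p1 and p2, the ratio of expected counts is (n × p1 × s)/(n × p2 × s) = p1/p2. The factor s cancels. There are fewer events, but neither formulation is favoured.

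**The case against.** The strongest reply is that nothing in the plan prevents headache from being recorded. The list is expressly not exhaustive, a general question is asked, spontaneous reports are accepted throughout, and 9.2 provides for specific questioning. The working prompts sit in the case report form (version 2.0 in SAP section 2), which was not available for review and may already name headache. All of this stands. A reader might infer that headache will be under-counted; the documents support only that it may be. What remains is that open wording permits a headache question without requiring one.

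A second reply is that no planned analysis is harmed. The objectives are pharmacokinetic with an exploratory microbiome aim, the adverse-event tables are descriptive, and no comparison of one symptom with another is planned. This also stands. It confines the point to how complete and readable the headache count is.

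A third reply is that the list fits other evidence in the protocol. Section 3 also relies on a three-year open-label epilepsy trial of 368 participants. Section 5.2 relies on studies at 4500 mg and 6000 mg and on a meta-analysis in which diarrhoea was the only adverse effect of CBD given alone. So a reader should not infer that the safety case rests on the single-dose study; that study is one part of it. The reply explains why gastrointestinal terms dominate. It does not explain why one of the three events named from that study is missing.

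A reader might also link the omission to withdrawal criterion iv in 6.10, "Use of over-the counter medications, health supplements or CBD products", reasoning that an unprompted headache leads to a painkiller taken at home and the loss of a completer. This does not follow. A named prompt at a scheduled time does not stop self-medication, and 6.10 says that withdrawn participants will be replaced.

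**Conclusion.** The point holds as a minor one. Headache is among the most common events in a study the protocol itself cites, yet it is not among the 11 symptoms asked about by name in either document. It can be captured by other routes, but may be under-recorded relative to nausea and somnolence, and the planned tables would not show it.

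The size of any loss is unknown, because the documents give neither a headache rate nor a capture fraction; the illustrative counts rest entirely on assumed values. The conclusion assumes that prompting by name raises reporting and that the case report form does not already contain a headache prompt. If it does, only the wording of the two documents needs aligning. The pharmacokinetic outcomes, sample size, power and alpha are untouched, and the comparison between formulations is not biased.

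**What to change.** Add headache to the named symptoms in protocol 7.5.3 and SAP 8.3. Check the case report form and add the prompt there if it is missing. The change is best made before the first dose; if it came mid-study, some participants would be prompted in one period only.

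The cost is one word in each document and at most one line on the form. The downside is a slightly longer enquiry and possibly a higher headache count, which should be borne in mind if the count is set against studies that relied on open questioning. If the list is left as it is, recording whether each event was prompted or volunteered would at least let a reader interpret the tables.

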7.5.4 Drug Effects Questionnaire (DEQ-5)

The DEQ-5 is questionnaire with five items, for example ‘‘Do you feel a drug effect, right now?’ with the response anchors ‘Not at all’ and ‘Extremely’ (Morean et al. 2013 [9]). It will be recorded on experimental visits at the following times: pre dose and at 1, 2, 4, 8, 24 and 48hrs post-dose.

7.5.5 Gastrointestinal Symptom Rating Scale (GSRS)

The GSRS is a 15-item rating scale which assesses five symptom clusters: reflux, abdominal pain, indigestion, diarrhoea and constipation. Each item is assessed with a 7-point Likert scale. The standard recall period for the scale is 7 days; this will be amended so that it assesses past 24 hours only. The scale will be used pre-dose and at 24 and 48 hours post dose. (28)

7.5.6 Stool Sample / Gut Microbiome (Exploratory analysis)

To assess the effect of the gut microbiome on the CBD’s pharmacokinetics and circulating endocannabinoid levels, a stool sample will be collected prior to each drug administration. Participants will be provided with stool sampling kits at the screening visit. This part of the study is optional.

7.6 Laboratory Procedures

At the screening visit, a blood sample will be taken to test for haematology (FBC) renal function (urea and electrolytes) and hepatic function (liver function tests, including bile acids). These tests will be repeated on experimental visits pre-dose and 4-hours post-dose on experimental visits. The test will be completed by ViaPath and be processed according to standard local procedures.

Urine samples for urinalysis, drug and pregnancy testing will be collected in standard collection pots. The samples will be disposed of as soon as tests are successfully completed.

At the screening visit, participants will be provided with pre-packaged and pre-addressed kits for at-home stool collection. Participants will be asked to mail stool kits before day 1 of each experimental

visits. Kits will be mailed to the Oxford Centre for Microbiome Studies for analysis on the gut microbiome.

On day 1 of each experimental visit, participants will have a venous cannula inserted for collection of blood samples. On days 2 and 3 of each experiment, for the 24 hour and 48 hour time-points, venepuncture will be performed a single sample will be taken. Blood samples will be collected in 5ml EDTA tubes.

Within 10min of collection, the samples will be centrifuged (3000rpm for 10minutes). The plasma will be decanted from the tube into two screw-cap collection tubes and immediately placed in a -20°C freezer in the CRF. The stored samples will be anonymised with participant ID, visit number and time point. Only the research team will be able to link ID number to participant details. At the end of each day, the samples will be moved to a -80°C freezer for longer term storage in the King's Clinical Trials Facility.

Only plasma will be stored so that analyses can be completed. No human tissue will be stored at the end of the research. Biological samples collected from participants as part of this trial will be transported, stored, accessed and processed in accordance with the 2004 Human Tissue Act.

